#### 7.3 The Randomisation Scheme

Randomisation will be on a 1:1 basis between the two treatment strategies, performed independently using minimisation to ensure groups are balanced for:

- a) NIV Outcomes score: low or medium risk
- b) Site
- c) HCO3-: <28 or ≥28

d) pH: <7.18 or ≥7.18
e) previous NIV: yes or no

#### 7.3.1 Method of implementing the randomisation/allocation sequence

An independent electronic randomisation service will be set up (sealedenvelope.com). Each site will have access to the randomisation service, the system will provide an immediate allocation, and the sponsor site (Northumbria Healthcare) will receive new randomisation alerts (including randomisation number and site) via email. Access to the randomisation service will be 24 hours a day, 365 days a year for the duration of recruitment.

#### 7.4 Blinding

As this is an interventional RCT comparing two weaning strategies, usual care clinicians and participants cannot be blinded to the trial. However, patient identifiable data will not be visible to the lead site (Northumbria Healthcare). All data collected will be anonymised to the statistician and health economist for the purpose of analysis.

#### 7.5 Emergency unblinding

Not applicable.

#### 7.6 Baseline Data

A separate source document worksheet (collecting the following data) and manual will be provided to all participating sites. The case report form is electronic (REDCap). Key data are shown in Table 1.

Table 1. Key data for source document worksheet.

Category	Data
Patient demographics	Name; NHS number. Hospital number; Gender; Age; Ethnicity; Multiple index of deprivation decile; Recruiting Site, Participant identifier generated at randomisation.
COPD diagnosis	Previous spirometry; Discharge spirometry (if required); Exacerbation history; NIV history; LTOT prescription; Covid-19 history; Previous lung surgery.
Admission indices	Date and time of arrival at hospital; Date and time clinician contacted to start NIV; Date and time NIV mask applied; Where NIV started and continued; Date and time patient moved to dedicated NIV area; Observations on arrival; Chest x-ray changes; ECG; Date and time of discharge from hospital; Mortality.
Risk stratification	NIV Outcomes score; eMRCD; DECAF; Apache II score; Charlson index.
Blood results	Full blood count indices.
Past Medical History	Various cardiovascular, respiratory and immunodeficiency variables.
Medication history	Bronchodilators, cardiovascular and antibiotic medications.
Social history	Home circumstances; smoking history; employment; Rockwood clinical frailty score; baseline function.
Blood gases	pH; PaCO 2 ; PaO 2 ; HCO 3 -; BE; SaO 2 .
NIV data	IPAP; EPAP/PEEP/CPAP; PS; Back up rate; Respiratory rate; Tidal volumes; Minute ventilation; Patient trigger, Interface used, Weaning plan; Complications; Date and time NIV removed; Relapse.

ISRCTN: 64639614 IRAS: 313485 CPMS: 53277

Observations	SpO2; Blood pressure; Heart rate; Temperature.
Randomisation	Standard weaning protocol; accelerated weaning protocol.
allocation	
Patient	Borg breathless scale; Phlegm visual analogue scale; Richards-
reported	Campbell sleep questionnaire; Hospital Anxiety and Depression scale; St
outcome	Georges Respiratory Questionnaire (COPD); EQ-5D-5L.
measures	
Trial outcomes	Readmissions; Mortality; Health economics (GP attendances;
	Emergency Department attendances; Readmission to hospital).

Respiratory Rate: **count** the number of breaths observed in 1 minute.

## 7.7 Trial Assessments

The following assessments will be completed during the acute phase of the trial.

Following confirmation of inclusion/exclusion criteria and informed consent, patients will undergo baseline assessment and randomisation. Baseline assessment will include sociodemographic details, full medical history, COPD history (confirmation of diagnosis and severity), details of index admission and NIV management.

On days 1 to 5, patients will be asked to complete the following assessments:

- 1) score their level of breathlessness on the Modified Borg breathless scale (score 0 not breathless at all to 10 maximal breathlessness);
- 2) their ease of sputum clearance on a visual analogue scale (score 0 very easy to 10 very difficult); and
- 3) their level of sleep quality via the Richards-Campbell questionnaire.

NIV status and weaning data will be recorded daily during admission.

Healthcare resource utilisation costs and mortality will be monitored during the in-hospital stay.

Spirometry will be performed pre-discharge if no previous spirometry confirming airflow obstruction is available.

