## 8.2 Intervention Arm: Accelerated weaning

The accelerated weaning protocol involves a daily 4-hour unsupported breathing trial with transcutaneous carbon dioxide tension (PtcCO2) monitoring throughout, and an ABG taken at the end of the 4-hour period.

Following randomisation, PtcCO2 monitoring is applied to the patient and sufficient time allowed to stabilise the trend of carbon dioxide (up to 20 minutes). Physiological measurements are recorded (RR, SpO2, FiO2, PtcCO2). The NIV mask is then removed from the patient (start of the 4-hour weaning trial), and once the patient is stable off NIV with oxygen titrated to SpO2 88-92%, the physiological measurements are repeated (10 to 30 minutes off NIV). If there are no signs of substantial clinical deterioration, and the PtcCO2 does not rise by >1kPa, then the physiological measurements will be repeated at 4 hours after NIV removal, and an ABG taken (end of the 4-hour weaning trial).

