#### 13.3 Patient and Public Involvement

We have sought the views of patients with COPD requiring NIV on the planned research, including: a) the importance of the clinical question; b) the trial design and burden of the assessments; and c) willingness to participate. Patients have found the assessments manageable, and have contributed to layout design, instructions and terminology used on the assessments.

The Northumbria Lung Research PPI COPD Group (NLRPG) have met twice in person to review this trial, the assessments required and all patient-facing documents. They will continue to meet regularly to discuss this trial, supported by our PPI lead, who will attend and feedback to the TMG, and assist the PPI group with dissemination of results. In response to feedback from the NLRPG, we will produce a video of a clinician reading the full patient information sheet as an alternative option of providing information about the study prior to consent. The NLRPG have also provided input into layout of modifiable assessments used in the trial design and have supported the importance of including the assessments asked during the acute phase. In particular, assessing quality of sleep as an outcome was highly important to the group.

In addition, real-time patient experience capture (following primary outcome) will inform our research. PPI activities will include: a) co-design of a PPI impact log to capture and evaluate the impact of PPI activities; b) ensuring study materials are appropriate for all potential participants by removing any equality, diversity and inclusion barriers; c) measurement of patient experience and thematic analysis of results for integration into trial results; and d) co-creation of a dissemination plan, and dissemination of results and PPI impact results to trial participants and people with COPD. Our patient research experience surveys to inform future PPI and trial conduct.

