#### 16. Appendices

Appendix 1: Schedule of Activities

## **Appendix 1: Schedule of Activities**

Schedule of Activities	Screening	Day 1*	Day 2 to 5	Pre- discharge	In-hospital stay	7 days post- randomisation	30 days post- randomisation	30 days post- discharge	90 days post- randomisation
Informed consent	X								
Inclusion/exclusion criteria	X	Х							
Demographic data	X								
Past Medical History	X								
COPD: diagnosis and severity	X								
Index admission and NIV details	X								
Modified Borg dyspnoea (breathlessness) scale		Х	X						
Sputum clearance		Х	X						
Richards-Campbell sleep questionnaire		Х	X						
NIV status and weaning data		Х	X		X				
Randomisation		Х							
Spirometry				X#			X		
Re-confirm consent				Χ			X		X
Hospital anxiety and depression scale						X			
St Georges respiratory questionnaire (COPD)						X	X		X
EQ-5D-5L (health-related quality of life)						Х	X		X
Healthcare utilisation cost							X		X
Mortality					X				X
Readmissions								X	

ISRCTN: 64639614 IRAS: 313485 CPMS: 53277

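### The Day 1 breathlessness, sputum and sleep ratings are counted as outcomes although randomisation is on Day 1 and their order relative to it is not fixed

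*Protocol*

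**What the plan says.** - **Schedule.** Section 7.7: "On days 1 to 5, patients will be asked to complete the following assessments". The third of these is "their level of sleep quality via the Richards-Campbell questionnaire". Appendix 1 marks the Borg scale, sputum clearance and the "Richards-Campbell sleep questionnaire" under Day 1 and under Day 2 to 5, with no mark under Screening. Its row for "randomisation" is marked only under Day 1.
- **Status.** Section 3.4 lists the three scales within secondary outcome 5. An asterisk there gives their timing as Day 1 to 5, and Day 1 is not set apart.
- **Baseline.** Section 7.7 says that after consent "patients will undergo baseline assessment and randomisation". It then lists the content: "Baseline assessment will include sociodemographic details, full medical history, COPD history (confirmation of diagnosis and severity), details of index admission and NIV management". None of the three daily scales is named.
- **Timing.** Section 7 requires inpatient assessments to be done on the day they are scheduled. No time of day is given for the daily ratings, and no recall period for the sleep questionnaire.
- **Analysis.** Section 10.3.3 gives a t-test or Mann-Whitney test for continuous outcomes. Change from baseline is mentioned only for SGRQ-C and EQ-5D-5L. No rule for combining the five days is stated.
- **Importance.** Section 13.3 reports that "assessing quality of sleep as an outcome was highly important to the group".

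**The concern.** A rating can serve as an outcome only if allocation could have influenced it, and as a baseline covariate only if allocation could not. The protocol does not let the analyst tell which applies on Day 1.

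For sleep, a rating completed on the day of randomisation would ordinarily refer to the preceding night, before allocated weaning had begun. The first night on which the arms can differ would then be rated on Day 2. For breathlessness and sputum, Day 1 contains consent, randomisation and, in the accelerated arm, the first removal of the mask. A score could fall on either side of these. The trial is open-label, so a score given after randomisation is given with knowledge of the allocation.

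At stake are the precision of the sleep comparison, which the patient group singled out, and the chance to use a pre-randomisation score of each scale as a covariate.

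**Working it through.** **1. Figures in the plan.** The protocol gives no figure for these scales. Its sample size of 164 concerns time to weaning. That figure reproduces within rounding: cause-specific hazard ratio 1.62, 135 events, 74 per arm, and 74 × 1.1 = 81.4, rounded up to 82 per arm. It has no bearing on this point beyond supplying group sizes.

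**2. Order of events on Day 1.** Appendix 1 puts randomisation on Day 1. Section 7 puts the Day 1 rating on that same day. Sections 8.1 and 8.2 start allocated weaning after randomisation. A sleep rating completed on Day 1 therefore cannot cover the night that follows. Exceptions are possible, such as daytime sleep or randomisation just after midnight. For Borg and sputum the same sections leave both orders open.

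**3. What averaging over Days 1 to 5 would do.** The following are assumptions and are not in the documents: the outcome is the mean of the daily ratings; each day has SD 1; any two days have correlation r; allocation has no effect on Day 1 and a constant effect d on Days 2 to 5.

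- Raw difference: (0 + 4d)/5 = 0.8d.
- Variance of a mean of m days: (1 + (m − 1)r)/m.
- Ratio of standardised effects, Days 1–5 to Days 2–5: 0.8 × SD₄/SD₅.
- Power, with d set so that Days 2–5 has 80% at two-sided 5%: Φ(2.80 × ratio − 1.96).

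At r = 0.5: SD₄ = √0.625 = 0.791 and SD₅ = √0.600 = 0.775. The ratio is 0.8 × 0.791/0.775 = 0.816, and power is Φ(2.80 × 0.816 − 1.96) = Φ(0.33) = 63%.

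**4. What adjustment for Day 1 would do.** Variance of the Days 2–5 mean given Day 1: (1 + 3r)/4 − r². At r = 0.5 this is 0.625 − 0.25 = 0.375. The standardised effect rises by √(0.625/0.375) = 1.29, and power is Φ(2.80 × 1.29 − 1.96) = 95%.

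| r | Ratio, Days 1–5 to 2–5 | Power, Days 1–5 | Power, Days 2–5 | Power, Days 2–5 adjusted for Day 1 |
|---|---|---|---|---|
| 0.3 | 0.831 | 64% | 80% | 88% |
| 0.5 | 0.816 | 63% | 80% | 95% |
| 0.7 | 0.808 | 62% | 80% | over 99% |

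The powers are the same for 74 and 82 per arm, because d is set to give 80% in each case.

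**5. The two gains kept apart.** In sample-size terms, dropping Day 1 is worth 1/ratio²: 1.45, 1.50 and 1.53 for r = 0.3, 0.5 and 0.7. Adjustment is worth a further 0.475/0.385 = 1.23, 0.625/0.375 = 1.67 and 0.775/0.285 = 2.72.

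**6. If each day is tested separately.** Days 2 to 5 are not diluted. The Day 1 sleep comparison is then merely one with no expected effect.

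**The case against.** The strongest objection is that the protocol does not say the five days are averaged. How repeated ratings are summarised, and which covariates are used, commonly belongs in the statistical analysis plan. This stands. A reader might infer that the sleep comparison is diluted as planned, but the documents do not support that; the loss is conditional on pooling.

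Second, it is an inference that the Day 1 sleep rating covers the night before randomisation. No recall period is stated, and the note belonging to the asterisk on the Day 1 column of Appendix 1 is missing from the text available for this review. The inference is reasonable given same-day completion, but it is not established.

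Third, a reader might say that all three scales lack a baseline. For sleep that does not fit the rest of the argument: if the rating precedes any allocation effect, a usable baseline is collected and only its label is wrong. The real gap in order concerns Borg and sputum. Section 7.6 lists these scales in a table under baseline data, but that table also holds readmissions and mortality, so it does not settle the order. The site worksheet and manual, which are not available here, might.

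Fourth, multiplying the two gains in step 5 gives 1.8- to 4.2-fold, and it would be tempting to charge all of it to the Day 1 label. Only about 1.5-fold comes from dropping Day 1; the rest is covariate adjustment. The constant effect is also doubtful. The protocol assumes median weaning times of 1.71 and 2.71 days, so the contrast between arms may narrow over the window.

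What survives is the order of data collection. A later analysis plan cannot recover whether a score was given before or after allocation if neither the order nor the time was fixed.

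**Conclusion.** The point holds as a gap in definition that costs precision. Section 3.4 counts Day 1 as outcome, Appendix 1 randomises on Day 1, and nothing orders the two. The Day 1 sleep rating is in effect a baseline carrying an outcome label, subject to the unstated recall period. Day 1 Borg and sputum scores may mix pre- and post-allocation values.

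If the days were pooled, the raw sleep difference would be 0.8 of its Days 2 to 5 value and power would drop from 80% to about 62–64%. This rests on assumed correlations of 0.3 to 0.7, no effect on Day 1 and a constant effect afterwards. With separate daily tests, Days 2 to 5 lose nothing.

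A reader might infer bias. The documents do not support that: including a rating without a treatment effect, or lacking a baseline covariate, weakens a randomised comparison but does not favour either arm. The primary outcome and the sample size are not affected.

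**What to change.** - Have the three scales completed on Day 1 after consent and before randomisation, and label them baseline.
- State the period that the sleep rating covers.
- Define the outcome as Days 2 to 5, analysed with the Day 1 score as covariate in place of the unadjusted t-test or Mann-Whitney test.
- Amend Section 3.4, Section 7.7 and Appendix 1 to match.

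The number of assessments does not change. The cost is a fixed order of procedures on Day 1, within the existing 24-hour limit for randomisation. In addition, no Borg or sputum score given after allocation on Day 1 itself would count as outcome.

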#### 7.8 Long-term Follow-up Assessments

The following assessments will be completed at set timepoints during the follow up phase of the trial.

- 7 days post-randomisation (within 10 days of the scheduled assessment): Hospital Anxiety and Depression Scale (HADS); St George's Respiratory Questionnaire for COPD (SGRQ-C); and EQ-5D-5L.
- 30 days post randomisation: Healthcare resource utilisation costs; SGRQ-C; EQ-5D-5L (within 10 days of the scheduled assessment); spirometry (30 days since last intercurrent exacerbation).
- 30 days post discharge: Readmissions.

ISRCTN: 64639614 IRAS: 313485 CPMS: 53277

- 90 days post randomisation: Healthcare resource utilisation costs; Mortality.
- 90 days post randomisation (within 14 days of the scheduled assessments): SGRQ-C and EQ-5D-5L

Informed consent will be reconfirmed at each assessment with participants pre-discharge from hospital, and at 30 and 90-days post-randomisation.

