#### 3.4 Secondary outcomes

- 1. Relapse requiring NIV (defined as recurrent AHRF>48 hours after removal of ventilator).
- 2. Total duration of ventilation.
- 3. Length of hospital stay.
- 4. NIV complications (incidence and severity).
- 5. Patient reported outcome measures: Modified Borg dyspnoea scale\*; Sputum clearance via visual analogue scale\*; Richards-Campbell sleep questionnaire\*; Hospital Anxiety and Depression Scale (HADS) pre-discharge; St Georges Respiratory Questionnaire for COPD (SGRQ-C) and EQ-5D-5L days 7, 30 and 90 post-randomisations.
- 6. Mortality in-hospital and 90-days post-randomisation.
- 7. Readmissions 30-days post-discharge.
- 8. Health economic analysis:
  - Costs to the NHS in terms of provision of the interventions (both on a respiratory support unit and a critical care unit) and cost implications of subsequent resource utilisation up to 90 days follow up;
  - Cost utility analysis using EQ-5D-5L quality adjusted life years (QALYs).
- 9. Responder analysis within the accelerated weaning group to identify predictors of success/failure.
- \*Day 1 to 5.

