#### 7. Trial Procedures

A schedule of activities is included in this application (appendix 1). All inpatient assessments will be completed on the scheduled day. Assessments within 30 days post-discharge from hospital will be completed within 10 days of the scheduled visit, in the patient's home, outpatient setting, or via telephone. Assessments within 90 days post-randomisation will be completed within 14 days of the scheduled visit, in the patient's home, outpatient setting, or via telephone.

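### HADS has two different time points, and the window for the day-7 questionnaires conflicts for patients still in hospital, so assessment time may be tied to discharge

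*Protocol*

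**What the plan says.** Four places in the protocol govern these questionnaires.

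- **Section 3.4** lists "Hospital Anxiety and Depression Scale (HADS) pre-discharge" and, in the same item, SGRQ-C and "EQ-5D-5L days 7, 30 and 90 post-randomisations". It also lists "Length of hospital stay" as a secondary outcome.
- **Section 7** has one rule for patients in hospital, "All inpatient assessments will be completed on the scheduled day", and another for those who have left: "Assessments within 30 days post-discharge from hospital will be completed within 10 days of the scheduled visit". The second rule allows a home visit, an outpatient visit or a telephone call.
- **Section 7.8** puts all three instruments, HADS, SGRQ-C and EQ-5D-5L, at one time point with one tolerance: "7 days post-randomisation (within 10 days of the scheduled assessment"). It does not mention whether the patient has been discharged, or whether the 10 days run before day 7, after it, or both.
- **Appendix 1** has one mark in the row "Hospital anxiety and depression scale". In the table as extracted, it stands in the column for 7 days post-randomisation, and the pre-discharge column is empty for that row.

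**The concern.** There are two faults.

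First, HADS cannot be both a pre-discharge and a day-7 measure unless discharge happens to fall at day 7. Sites that follow section 3.4 and sites that follow section 7.8 would collect it on different days. A pre-discharge HADS is also timed by an event after randomisation, and the time to that event is itself an outcome. The arms might then be compared at different stages of recovery.

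Second, a patient still in hospital on day 7 falls under two rules: no tolerance in section 7, 10 days in section 7.8. If the section 7 rule is applied, the tolerance depends on whether the patient has gone home, so discharge again helps to decide when the measurement is taken.

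The outputs at stake are the HADS comparison, the early SGRQ-C and EQ-5D-5L values, and the first point on the EQ-5D-5L curve used for QALYs. Appendix 1 shows no SGRQ-C or EQ-5D-5L before day 7, yet section 10.3.3 plans a mean change from baseline, so the day-7 value may have to serve as the starting value. The trial is open-label, so whoever chooses a date within a wide window may know the allocation.

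**Working it through.** The protocol gives no figure to reproduce here. The check sets the rules side by side, works out the windows, and gives a range for the possible difference in timing.

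**HADS.** Section 3.4: pre-discharge. Section 7.8: day 7. Appendix 1: a single mark, at day 7. Two places agree and one does not. This conclusion needs no assumption.

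**Windows.** These are nominal day ± tolerance, from section 7.8, if the tolerance runs both ways:

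- Day 7: 7 − 10 = −3 to 7 + 10 = 17
- Day 30: 30 − 10 = 20 to 30 + 10 = 40
- Day 90: 90 − 14 = 76 to 90 + 14 = 104

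The three windows do not overlap. However, the day-7 tolerance is longer than the interval it applies to, and its early end would precede randomisation. Read as late-only, the window is day 7 to day 17.

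**Which rule applies on day 7**

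| Patient on day 7 | Section 7 governs | Section 7.8 governs (late-only) |
|---|---|---|
| Still in hospital | day 7 only | day 7 to 17 |
| Discharged | up to day 17 | day 7 to 17 |

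Under section 7, the latest permitted dates differ by 17 − 7 = 10 days according to discharge status. Under section 7.8 they do not differ.

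**Possible difference between arms if section 7 governs.** Inpatients have no delay, so if the mean delay among discharged patients is the same in both arms:

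shift in mean assessment day = (difference between arms in the proportion discharged by day 7) × (mean delay among discharged patients)

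The documents give neither input. Both are assumed and varied:

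| Difference in proportion discharged | Mean delay 2.5 days | 5 days | 10 days |
|---|---|---|---|
| 0 | 0 | 0 | 0 |
| 0.10 | 0.25 | 0.5 | 1.0 |
| 0.20 | 0.5 | 1.0 | 2.0 |
| 0.30 | 0.75 | 1.5 | 3.0 |

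The 10-day column is the extreme, with every discharged patient assessed on the last permitted day. Turning these days into questionnaire points or utility would need a daily rate of recovery, which the protocol does not give, so no such figure is offered.

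**Weight of day 7 in the QALY.** With straight lines between days 7, 30 and 90, the day-7 value carries (30 − 7)/2 = 11.5 of the 83 days from day 7 to day 90. If a day-0 value were also used, it would carry (30 − 0)/2 = 15 of 90 days.

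**The case against.** The strongest reply is that section 7.8 is the specific rule and section 7 the general one. The protocol separates the acute phase (section 7.7, days 1 to 5) from the follow-up phase (section 7.8) and puts the day-7 questionnaires in the latter with their own window. On that reading every patient has the same window and nothing depends on discharge. This is a fair reading, and it is why the unequal window cannot be stated as fact. It does not remove the conflict: section 7 says all inpatient assessments, and a day-7 questionnaire completed on the ward is one. Nor does it touch the HADS contradiction.

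A reader might go further and infer that accelerated patients will go home earlier, be assessed later in recovery, and look better for that reason alone. The documents do not support this:

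- Section 10.1 assumes weaning 24 hours earlier, not discharge 24 hours earlier.
- Section 2 mentions savings from a shorter hospital stay only conditionally.
- Section 4 declares equipoise and allows that accelerated weaning may bring more relapse requiring NIV, which could delay discharge.
- The direction is open in any case. If day 7 stands in for baseline, a later first value could shrink the apparent improvement rather than enlarge it.

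Two further points reduce the weight. A window is a tolerance, not a planned delay, and with telephone contact allowed after discharge the average delay may be short. Section 10.9 says that QALYs will be adjusted by time, which may already mean actual dates, although the text does not say so. Both points stand as limits on size.

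**Conclusion.** The concern holds as a matter of conflicting rules. HADS is pre-discharge in one place and at day 7 in two others, and sections 7 and 7.8 disagree about inpatients on day 7. Both conclusions follow from the text alone.

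A difference in timing between the arms is conditional. It arises if HADS is collected before discharge, or if section 7 governs the day-7 forms, and in either case only if discharge timing differs by arm. The protocol treats such a difference as possible but neither states nor quantifies it. For the day-7 forms, the shift in mean assessment day is zero with no discharge difference and 0.25 to 3.0 days under the assumed inputs above. Neither the size nor the direction of any bias in the scores can be established from the documents.

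The reach is limited to HADS, SGRQ-C, EQ-5D-5L and the QALY. The primary outcome and the sample size are unaffected. The change is worth making because it is cheap and removes a dependence on an event after randomisation.

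**What to change.** 1. In section 3.4, move HADS from pre-discharge to day 7 post-randomisation. Section 7.8 and Appendix 1 already say this and need no change on the point.
2. Reconcile sections 7 and 7.8 to a single day-7 window that runs forward only, is clearly shorter than 10 days, and is the same for inpatients and discharged patients. Section 7 already allows telephone completion after discharge.
3. Record the actual date of each questionnaire, and state in section 10.9 that this date is the time used in the EQ-5D-5L area under the curve.

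The cost is a wording amendment and a date field if there is none. The downside is a few more missing day-7 forms, because a shorter window leaves less time to reach patients who have gone home.
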